## STATEMENT OF COMPLIANCE

The study will be conducted in accordance with the International Conference on Harmonization guidelines for Good Clinical Practice (ICH E6), the Code of Federal Regulations on the Protection of Human Subjects (45 CFR Part 46). All personnel involved in the conduct of this study have completed human subject's protection training.

[figure not shown]

## LIST OF ABBREVIATIONS

AE	Adverse Event/Adverse Experience
CFR	Code of Federal Regulations
CRI	Clinical Research Institute
DFW	Dallas-Fort Worth
CRF	Case Report Form
DHHS	Department of Health and Human Services
DSMB	Data and Safety Monitoring Board
EVALI	E-cigarette or Vaping Product Use-Associated Lung Injury
FDA	Food and Drug Administration
GCP	Good Clinical Practice
ICH	International Conference on Harmonization
IHE	Inside Higher Ed
IRB	Institutional Review Board
NPR	National Public Radio
US	United States

## 1. INTRODUCTION

### 1.1. Background:

Adolescent use of vaporizers has increased rapidly in recent years in the United States. According to a survey taken by the National Public Radio (NPR) in November 2019, vaping amongst high school students has increased since 2016, in which approximately 12 percent of high school students reported using vaping products compared to 28 percent in 2019 (NPR, 2019). NPR stated that as of 2019, 5.3 million teenagers use e-cigarettes daily (NPR, 2019). According to American Lung Association, about 40 percent of kids have tried vaping. Further, it is likely their parents do not know as vaping is easy to hide compared to traditional cigarettes (American Lung Association, 2019).

Unfortunately, vaping does not stop after high school. Vape usage has increased on college campuses even with nationwide smoking bans on every campus. According to a survey done by Inside Higher Ed, it was found that the use of- e-cigarettes, vape marijuana, and vape nicotine has doubled among college students between the years of 2017 to 2018 (IHE, 2019). However, the use of vaporizers in the adult (25 to 44) age group is lower compared to the younger population due to the recent popularity of vaping products (Truth Initiative, 2019).

Vape products contain aerosol and approximately 7,000 chemicals; at least 70 of these chemicals are known to cause cancer (American Cancer Society, 2018). Due to nicotine being a highly addictive substance and prominent in many vaping products, individuals that smoke vape pens are four times more likely to

use tobacco products and smoke cigarettes (Truth Initiative, 2019). E-cigarettes or vaping products use- associated lung injury (EVALI) has been reported. Many individuals are being diagnosed with cancers of the lung, mouth, bronchi, and throat.

The Centers for Disease Control and state agencies have reported 2,506 lung injury cases that required hospitalization and 54 deaths linked to vaping as of December 2019 (CDC, 2019). According to John Hopkins, on January 7, 2020, there were 57 deaths that were linked to vaping. That number increased to 60 on January 21, 2020 (John Hopkins, 2020)

Many vaping companies present their products as nicotine free and as being a safe and non-addictive way of smoking. From commercials to online ads, consumers are being told that this product is free from the smell of cigarettes, reusable, much cheaper, and even healthier than traditional cigarettes. This information can be very deceiving and persuasive to the young mind.

This program titled, “To Vape or Not to Vape”, will provide education to adolescents and young adults about the potential risk of vaping in an effort to assist with lowering the usage rates within the population. Content will include information about current statistics, potential short-term and long-term side-effects, and healthy alternatives for dealing with stress and peer-pressure. We anticipate that this program will increase this population’s knowledge about the risks of vaping products, and deter them from future use of the products. Effectiveness of this program will be measured by pre and post-tests.

**1.2.** Aim(s)/Objective(s)

The overall goal of this study is to increase knowledge of vaping and its associated risks. This study will find the patterns of vaping, and how it all started among adolescents. We want to know if students are aware of the serious and long term effects of vaping.

The objectives are:

1. To provide at least 100 middle school and high school students with anti-vaping education.
2. To provide at least 40 college students with anti-vaping education.
3. To improve the overall knowledge of vaping statistics and side effects as measured by a pre and post-test. The pre-test will be the baseline measurement. The post-test will be the measure of effectiveness. Out of the 10 questions on the post-test, the goal is to have the students answer at least 8 out of the 10 questions correctly.
4. To decrease the percentage of students who say that they are likely to vape in the future.

The program will be going to middle school, high school, and college campuses in the Dallas-Fort Worth (DFW) area to speak with students about vaping. The program will be implemented by community outreach, as the students will be presented with information about vaping and the resources necessary to prevent or stop vaping. This program will present the students with a 35-minute curriculum that is listed below. The purpose of this study is to relay

and publish data that will support education about vaping and the many health risks associated with vaping products.

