### **1.4.** Hypothesis

We believe this program will make at least 50 percent of the participants more aware of the dangers and consequences of vaping, potentially lowering the rates of those participating in this habit while also preventing others from starting.

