## **3. STUDY DESIGN**

The time frame for this study will be approximately one month, with the first presentation of the program being in March 2020. This program will be provided to high school and college students within the Dallas Fort Worth metroplex. The program will be implemented by community outreach, as the students will be presented with information about vaping and the resources necessary to prevent or stop vaping from their daily lives. The purpose of this study is to relay and publish data that will support the education of vaping and the many health risks associated with vaping products.

During this program, we will be presenting to 20 to 30 students at a time in a classroom setting, which will allow us to closely interact with participants. This is an anonymous study; therefore, all participants' names will not be listed nor stated in any documentation. In order to accurately complete this anonymously while also calculating our results, students will be asked to list their age, gender, race, and zip code on their survey. This program will be approximately 35 minutes. Participants will be given a pretest (Appendix C) before any information is presented. Students will be given an incentive to complete this program. Below is an outline (Appendix D) of the program:

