## **IV. Post test**

Program Component	Intro/ Pre-test	History of vapes	Chemical in vapes, and reaction to inside the body	Mental Health	How to change addictive behaviors	Resources	Questions / Recap	Post-test
Brief Description	Introducing the program to the targeted population and having the students take a 5 minute pre-test.	Students will learn about the history of vapes and tobacco.	Students will learn about nicotine and its addictive properties. Students will learn how these things affect the lungs, heart, and teeth	Students will learn how the brain functions and how it reacts to contents in vapes.	Helping the students identify their triggers and learning behaviors to change their point of view.	Providing the students resources within their community	Going back over the main bullet points from the curriculum and letting the students ask questions	Students will take a 5 minute post-test
Duration (in minutes)	5	3	5	3	5	3	5	5

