## 5. STATISTICAL CONSIDERATIONS

## 5.1. Sample Size Considerations

A power analysis using the G-power 3.1 computer program (Faul & Erdfelder, 2009) indicated that a total sample of 35 people would be needed to detect a medium effect (Cohen's  $dz = 0.5$ ) with 80% power using matched-pairs Wilcoxon signed-rank test with alpha at 0.05 and assuming non-normal distribution. We need to enroll at least 44 subjects to account for 20% attrition rate. We plan to enroll 100 subjects in this study from whom we will collect pre- and post-test data on vaping.

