## Appendix B: Data Collection Tool

## Excel Spreadsheet: Pre-Test

## Excel spreadsheet: Post-Test

## Appendix C

### Pre-Test

1. Do you or have you ever smoked tobacco cigarettes?
  - a. Yes, I currently smoke
  - b. Yes, I smoked in the past
  - c. No, I never smoked
2. Do you or have you ever used a vape pen, e-cigarette, or other vaping products?
  - a. Yes, I currently use these products
  - b. Yes, I have tried these products in the past
  - c. No, I never used these products
3. How often do you vape?
  - a. Everyday
  - b. 3 to 5 times a week
  - c. Once a week
  - d. Few times a month
  - e. Never
4. How long have you been vaping and/or using tobacco products?
  - a. Less than 3 months ago
  - b. 6 months ago
  - c. About 1-2 years ago
  - d. More than 2 years ago
  - e. I never have
5. Using vaping products will help you stop smoking cigarettes?
  - a. True
  - b. False
6. Using vaping products may cause harm to my health?
  - a. True
  - b. False
7. By using vaping products, I am more likely to smoke cigarettes in the future.
  - a. True
  - b. False
8. There are currently \_\_\_\_ million students that use vaping products
  - a. 1 million
  - b. 3.5 million
  - c. 8 million
  - d. 5.3 million
9. Students who vape are \_\_\_\_ more likely to begin smoking cigarettes
  - a. twice

b. four times  
c. five times  
d. ten times

10. There are at least \_\_\_\_ confirmed vape related deaths as of January 21st, 2020  
a. 15  
b. 35  
c. 60  
d. 2

11. People vape because \_\_\_\_  
a. It helps them to relax  
b. Their friends or family vape  
c. They like the taste of it  
d. They think it is safer than tobacco cigarettes  
e. All the above

12. I feel pressured to vape.  
a. Yes  
b. No  
c. Sometimes

13. Effects that vaping has on my body are \_\_\_\_  
a. Decreased brain development  
b. Problems with breathing  
c. Increase heart rate  
d. Higher chance of developing cancer  
e. All the above

14. How likely are you to use vaping products?  
a. Not at all  
b. Not sure  
c. Very likely  
d. I already vape

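### The pre/post gain shows only immediate end-of-session knowledge on repeated items; it cannot support the plan's statements on future use, prevention or a fall in vaping

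*Combined protocol and SAP*

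**What the plan says.** Section 1.1 states "Effectiveness of this program will be measured by pre and post-tests", and objective 3 in 1.2 assigns the roles: "The pre-test will be the baseline measurement. The post-test will be the measure of effectiveness". Neither section names any other measurement of effect.

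Section 3 puts both tests in one classroom session: "This program will be approximately 35 minutes". In its component table the slot before the post-test is for questions and recap, described as "Going back over the main bullet points from the curriculum and letting the students ask questions". The last slot reads "Students will take a 5 minute post-test".

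Several sections look beyond the session:
- 1.1 expects the program to deter later use.
- 1.4 speaks of "potentially lowering the rates of those participating in this habit while also preventing others from starting".
- 1.4.1 (primary hypothesis) predicts a 5% decrease in users and says a pre and post survey will measure the program's goal. The conclusion in Appendix D gives a 5 percent reduction in students who vape as part of that goal.
- 2.2.1 hopes for lower use in the area within 6 months, while section 3 gives the study about one month.

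Section 5.2 plans paired t, Wilcoxon signed-rank and McNemar tests only.

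**The concern.** A paired before/after difference in a single group is the sum of everything that changed between the two tests. Here that includes the teaching and also the experience of having just answered the same questions. Students who have met an item may listen for its answer, or ask for it in the question slot.

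Three of the repeated items ask for an exact figure: the number of student users, the multiple for starting cigarettes, and the count of deaths. All three figures appear in 1.1. The teaching outline in Appendix D states none of them, although 1.1 promises current statistics. A prompted question is thus one way the answers could reach the class.

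The second issue is the time horizon. A score taken in the same half hour says nothing direct about what is remembered later or about behavior. If the sponsor publishes a significant gain as program effectiveness, readers of 1.4, 1.4.1 and 2.2.1 would take it as evidence that vaping falls or is prevented. The study collects no data that could show this.

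**Working it through.** **1. Interval between the tests (section 3 table).** The slots, in minutes, are pre-test 5, history 3, chemicals 5, mental health 3, changing behaviors 5, resources 3, questions and recap 5, post-test 5.
- Total: 5+3+5+3+5+3+5+5 = 34, which agrees with the stated length of about 35.
- End of pre-test slot to start of post-test slot: 3+5+3+5+3+5 = 24.
- End of recap slot to start of post-test slot: 0.

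**2. Item overlap (Appendix C).** Post-test item k has the same wording as pre-test item k+4, for k = 1 to 10. For example, pre-test item 10 and post-test item 6 both ask about "confirmed vape related deaths as of January 21st, 2020" with the same four options. The overlap is 10 of 10 post-test items. Pre-test items 1 to 4, on smoking and vaping history and frequency, are dropped.

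**3. What each post-test item can show.** Item 8 (pressure) and item 10 (likelihood of use) are not knowledge items. Item 10 records intention. Its last option lets a student declare current vaping, but an answer given the same half hour cannot register a change in use. The direct questions on current use and frequency (items 2 and 3) are on the pre-test only. The 5% decrease therefore has no follow-up value, and nothing is scheduled that could observe use at 6 months.

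**4. The plan's own sample size, reproduced first.** For the signed-rank test I used the noncentral t with the relative efficiency for normal data, 3/π: effective n = n × 3/π, degrees of freedom = effective n − 1, noncentrality = dz × √(effective n), two-sided alpha 0.05.
- n = 35, dz = 0.5: effective n = 33.42, noncentrality = 0.5 × 5.781 = 2.89, power 0.801. The stated 35 reproduces.
- Attrition: 35 / (1 − 0.20) = 43.75, rounded up to 44, as in "We need to enroll at least 44 subjects to account for 20% attrition rate". The sample size is not in dispute.

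**5. Could a testing effect alone give a significant result?** The documents give no retest effect, so these values are assumptions. With 100 complete pairs (the enrollment in 5.1), effective n = 95.49 and noncentrality = 9.772 × dz.

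| Assumed shift from repeated testing alone (dz) | Probability of p < 0.05 |
|---|---|
| 0.1 | 0.16 |
| 0.2 | 0.49 |
| 0.3 | 0.83 |

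This treats students as independent. It does not show that such a shift exists, only that the planned test could not tell one from a teaching effect.

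**The case against.** **The design delivers objective 3.** Read literally, objective 3 asks only for better knowledge from pre-test to post-test. A single-session evaluation is a common and feasible choice for outreach, and repeating the items is what permits a paired analysis. This stands. The fault is in what other sections attach to the result.

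**The wider statements are soft.** Section 1.4 says potentially, and 2.2.1 expresses a hope. That is fair for those two. It does not cover 1.4.1, which predicts a 5% decrease and names the survey as the measure.

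**Carry-over is conjecture.** No section says students are told that the items will return, and the question slot appears only in the section 3 table; Appendix D has a presenter's conclusion before the post survey. This stands too. A reader might infer that part of the gain is certainly an artifact, or that it would vanish in classes taught without a pre-test. The documents support neither. They give no retest effect, they do not describe use without a pre-test, and section 3 lists the pre-test as a program component.

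**Should the design be changed to measure carry-over?** A reader might infer that half of each class should skip the knowledge items at pre-test. With 50 against 50, the 95% half-width is 1.96 × √(1/50 + 1/50) = 0.39 SD, and at 40 against 40 after 20% attrition it is 1.96 × √(1/40 + 1/40) = 0.44 SD. Half the students would lose their knowledge baseline for that coarse estimate. The recap is also class-wide, so both halves would hear the same answers and neither score would be free of carry-over. I do not recommend it.

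**Conclusion.** The point holds as a limit on interpretation. The 24-minute interval, the 10 of 10 repeated items, and the absence of a comparison group or later measurement all come directly from the documents. The paired gain can show immediate end-of-session knowledge and, for item 10, immediate stated intention. It cannot show retained knowledge, prevention of starting, a fall in users or a decline within 6 months.

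A testing effect is possible and inseparable from teaching under 5.2, but its size cannot be derived from the documents; the probabilities in the table rest on assumed shifts. It would go too far to infer that the program does not work or that the gain is mostly artifact.

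**What to change.** In 1.2 (objective 3), 1.4, 1.4.1, 2.2.1 and 2.2.2:
1. Name the knowledge outcome *immediate end-of-session knowledge* and the item 10 outcome *immediate stated intention*.
2. State that no conclusion on retained knowledge, vaping rates or prevention will be drawn from the pre/post comparison.
3. In 1.4.1, remove the statement that the 5% decrease is measured by the pre and post survey.
4. State that all post-test items were seen earlier in the same session, and report the possible testing effect, of unknown size, as a limitation.

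This changes wording only: no new form, session, staff time or loss of sample size. Section 6.2 requires IRB review of any amendment. If the protocol is already approved, the section 10 fee for an amendment without revised consent applies: $345, or $345 × 1.30 = $448.50 with indirect cost.

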**2. OBJECTIVES AND STUDY OUTCOME MEASURES**

**2.1.** Study Objectives

**2.1.1.** Primary Objective(s)

The primary objective for this program is to obtain an understanding and gather information on the percentage of vape users in teens and young adults. This study will include at least 100 individuals, as this will allow us to determine why vaping is so prominent, what causes individuals to be attracted towards this habit, and determine why there is an increasing rate of vaping.

**2.1.2.** Secondary Objective(s)

The secondary objective for this program is to prevent those who do not vape to not begin to partake in this habit and to reduce the percentage pf the target population who are currently vaping, by increasing their knowledge on the dangers of vaping by 10%.

**2.2.** Study Outcome Measures

**2.2.1.** Primary Outcome(s)

We will obtain the percentage of vape users and their reasons for vaping from information gathered from pre-test (Appendix C). Within 6 months, we hope to see a decline in the usage of vapes in the DFW area.

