### 2.2.2. Secondary Outcome(s)

Changes in the degree of understanding will be assessed from the results of the pre- and post-test (Appendix C). In addition, we hope to find the answers to the following questions:

- Is vaping within the student's environment?
- Are the students being socially peer pressured into smoking, and if so how often?
- Are most students forming addictive behaviors towards vaping?
- What are the triggers that cause a student to vape?
- What is their reasoning on why they vape or participate in any smoking products?
- Do members of their close group of friends' vape?
- Are students aware of the serious and long-term side effects of vaping?

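### Objective 3 sets a post-test-only goal of 8 of 10, so students already at the threshold before teaching count toward it, and the goal does not match the paired change the plan analyses

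*Combined protocol and SAP*

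**What the plan says.** Objective 3 (section 1.2) opens with an aim about improvement: "To improve the overall knowledge of vaping statistics and side effects as measured by a pre and post-test". It continues "The pre-test will be the baseline measurement", then "The post-test will be the measure of effectiveness", and ends with the numerical target: "the goal is to have the students answer at least 8 out of the 10 questions correctly". The target applies to the post-test. It carries no condition on the pre-test score, and no share of students who must reach it is given.

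Elsewhere the plan speaks of change. The background section says "Effectiveness of this program will be measured by pre and post-tests". Section 2.1.2 aims to act on vaping "by increasing their knowledge on the dangers of vaping by 10" percent. Section 2.2.2 says "Changes in the degree of understanding will be assessed from the results of the pre- and post-test (Appendix C". Section 5.1 sizes the study on a matched-pairs Wilcoxon signed-rank test. Section 5.2 lists the paired t test, the Wilcoxon signed-rank test and the McNemar test by type of outcome, without naming the 8-of-10 goal.

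Section 1.4 adds a further target: "We believe this program will make at least 50 percent of the participants more aware of the dangers and consequences of vaping". It gives no score, minimum change or reference value.

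**The concern.** A post-test level mixes what the session taught with what students brought into the room. A class that arrives well informed can meet the 8-of-10 goal with nothing learned, and a class that learns a lot from a low start can miss it. There is no control group, so the pre-test is the only reference for an effect, and the goal as worded does not use it.

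At stake is the statement that will be published. A report could say what percentage of students met the program's goal, in keeping with objective 3, and readers would take that percentage as the effect of teaching. Section 5.2 would not prevent this, because it does not say which outcome answers objective 3.

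**Working it through.** **1. The plan's own figure.** Inputs from section 5.1: dz = 0.5, 80% power, alpha 0.05, Wilcoxon signed-rank test, 20% attrition. I took two-sided alpha and a normal parent distribution, for which the relative efficiency is 3/π = 0.955. Noncentral-t power with effective size 35 × 0.955 = 33.4 is 0.801, and 35 is the smallest n that reaches 80%. Attrition: 35 / 0.8 = 43.75, so 44. Both stated figures reproduce. They concern a paired change, not the 8-of-10 level.

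**2. Which items can be scored.** The ten post-test items (Appendix C) repeat pre-test items 5 to 14. Post-test item 8 (feeling pressured) and item 10 (likelihood of use) have no correct answer. Eight knowledge items remain: three true/false, three with four options and two with five. A goal of 8 correct may therefore mean 8 of 10 items or all 8 scorable items. I show both.

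**3. Share at the threshold with no teaching.** The documents give no baseline knowledge level, so p, the chance that a student answers an item correctly, is an assumption, with items independent.

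- 8 of 10: P = 45p⁸(1−p)² + 10p⁹(1−p) + p¹⁰. At p = 0.7 this is 0.2335 + 0.1211 + 0.0282 = 0.383.
- 8 of 8: P = p⁸. At p = 0.7 this is 0.058.

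| Assumed p | 8 of 10 | 8 of 8 |
|---|---|---|
| 0.6 | 17% | 1.7% |
| 0.7 | 38% | 5.8% |
| 0.8 | 68% | 17% |

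With no learning, the expected share is the same at pre-test and post-test, so the expected paired difference is zero in every row. The post-test share alone shows the figure in the table.

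**4. Secondary point, section 1.4.** Suppose being more aware were read as scoring higher on the post-test. With no learning and fresh independent guesses each time, P(post > pre) = (1 − P(tie)) / 2.

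- Only the three four-option items guessed: the scores 0 to 3 have probabilities 27/64, 27/64, 9/64 and 1/64. P(tie) = (729 + 729 + 81 + 1)/4096 = 0.376, so 31.2% rise.
- All eight items guessed: P(tie) = 0.219, so 39.1% rise.

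An equal share falls, so improved minus worsened has expectation zero. The binomial chance that at least half the students rise by guessing alone is:

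| Share rising by chance | n = 44 | n = 100 |
|---|---|---|
| 31.2% | 0.7% | 0.007% |
| 39.1% | 9.3% | 1.7% |

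**5. The two mechanisms are separate.** Prior knowledge inflates the 8-of-10 goal, but a student with a perfect pre-test cannot score higher. Guessing matters for a count of students who improve, but guessing all eight items correctly has probability (1/2)³(1/4)³(1/5)² = 1/12,800.

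**The case against.** The strongest reply is that objective 3 should be read whole. Its aim is to improve knowledge, it names the pre-test as baseline, and the background section measures effectiveness by both tests. The sample size, the secondary outcome and every test in section 5.2 are paired. In a paired analysis, symmetric guessing cancels and a student at ceiling contributes no change. If 8 of 10 is treated as a categorical outcome, section 5.2 already assigns the McNemar test. On this view the goal is only an attainment target added to a sound analysis.

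Much of this stands. A reader might infer that the plan judges effectiveness by the post-test level alone, and the documents do not support that. What remains is that the sentence naming the measure of effectiveness, and the only number in the objective, refer to the post-test. No section says that the threshold share will be compared with its pre-test value.

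Two other inferences also go too far. One is that section 1.4 is a rule counting only students who gain. It states an expectation, never linked to a score, and the score reading is tested above only as a possibility. The other is that success could be declared on either target with little or no effect. Guessing alone rarely brings the share to 50%, and objective 3 states no required share, so the percentages in step 3 cannot show that success would be declared.

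**Conclusion.** The concern holds as a mismatch between a stated goal and the planned analysis. Followed as written, the 8-of-10 goal credits prior knowledge to the program. The size depends on a baseline knowledge level that the documents do not give: 17% to 68% of students at the threshold without teaching for a literal 8 of 10, or 1.7% to 17% if all eight scorable items are needed, for p from 0.6 to 0.8 and independent items. The literal reading treats all ten items as scorable, which two of them are not, so the lower range may be the relevant one.

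For section 1.4 the finding is smaller: the term is undefined. If it came to mean a higher score, 31% to 39% of students would qualify by guessing alone under the two scenarios in step 4, so the reported share would overstate learning. The chance that guessing alone reaches the 50% target is 1.7% or less at the planned 100 students.

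The paired analyses in section 5.2 are suitable for the question and need no replacement. Without a control group they cannot separate learning from familiarity with repeated items. Rewording objective 3 does not change that.

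**What to change.** **Section 1.2, objective 3.** State that effectiveness is judged by the within-student change from pre-test to post-test on the shared knowledge items (pre-test 5 to 11 and 13; post-test 1 to 7 and 9). State what the threshold of 8 means when two of the ten items have no correct answer. Report the share at the threshold at both tests, with the McNemar test already in section 5.2. Add the paired difference, (students moving up to the threshold − students falling below it) / n, with its 95% CI. The share reaching the threshold among students below it at baseline may be shown as description only, because a group selected for low scores tends to rise on retest.

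**Section 1.4.** Define the term. If it means a higher post-test score, report improved, unchanged and worsened, and base the claim on improved minus worsened with a 95% CI.

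**Cost.** Wording in two sections and one extra table, from data already collected. The quoted success figure will be smaller. Each student's two tests must be linked, as the paired tests in section 5.2 already require. The documents list only age, gender, race and zip code (section 3) and zip code and grade level (section 6.3) for this, so the means of linking should be confirmed.
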